1. Has met criteria at any time during their life for a primary psychotic disorder (e.g. schizophrenia), or dementia.
2. Meets criteria for DSM-5-defined substance use disorder within three months of the screening visit.
3. Currently taking two or more antidepressants.
4. Presents with a clinically significant suicide risk, as assessed by a study physician.
5. Presence of any unstable or central nervous system-related medical illness that would interfere with cognition or participation.
6. Women who are currently pregnant or lactating, or plan to become pregnant during the study.

Setting

The setting of the study will occur in the Mood and Anxiety Disorders Program research clinic at the Emory University Executive Park campus.

Recruitment

Patients will be recruited through advertisements and clinician referral.

Procedures

The study consists of four visits.

Visit 1.

Visit 1 commences with the informed consent discussion and signing the informed consent form for the study. Subsequently, the following procedures will be performed:

1. Demographic information
2. Psychiatric interview and MINI.
3. Clinician ratings of symptoms: MADRS, HAMA
4. Clinician rating of suicidality: CSSRS
5. Clinician assessment of discontinuation symptoms present at baseline: DESS
6. Vital signs (temperature, height, weight, blood pressure, pulse)
7. Urine pregnancy test for women of child-bearing potential.
8. Medical History
9. Past psychiatric treatment history
10. Review of concomitant medications and supplements
11. Review of recall of side effects experienced when starting the antidepressant.
12. Patient questionnaires: DEBS, Q-LES-Q, BIS

Participants with internet access, either by cell phone or computer, will be asked to record their mood symptoms daily on the self-report Scale for Anxiety and Depression (SAD). This is a free internet app available at sad.ecu.edu.

Participants will use their de-identified study ID code as their login name to preserve confidentiality. After completing the scale in the office at Visit 1, participants will complete the SAD daily until Visit 4. Participants who lack internet access will be given paper versions of the form to fill out each day.

Upon completion of these components, the patient will be randomized to either Taper A or Taper B (see below). The physician will discuss the tapering process with the patient.

Visit 2

Visit 2 occurs 1 week after initiating the antidepressant taper. The following procedures will be performed:

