1. Clinician ratings of symptoms: MADRS, HAMA
2. Clinician rating of suicidality: CSSRS
3. Clinician assessment of discontinuation symptoms: DESS, PWC-20
4. Vital signs (temperature, height, weight, blood pressure, pulse)
5. Review of concomitant medications and supplements
6. Review of adverse events

7. Patient questionnaires: DEBS, BIS, PGI-C

Visit 3:

Visit 3 occurs 2 weeks after initiating the antidepressant taper. The following procedures will be performed:

1. Clinician ratings of symptoms: MADRS, HAMA
2. Clinician rating of suicidality: CSSRS
3. Clinician assessment of discontinuation symptoms: DESS, PWC-20
4. Vital signs (temperature, height, weight, blood pressure, pulse)
5. Review of concomitant medications and supplements
6. Review of adverse events
7. Patient questionnaires: DEBS, BIS, PGI-C

Visit 4:

Visit 4 occurs 3 weeks after initiating the antidepressant taper. The following procedures will be performed:

1. Clinician ratings of symptoms: MADRS, HAMA
2. Clinician rating of suicidality: CSSRS
3. Clinician assessment of discontinuation symptoms: DESS, PWC-20
4. Vital signs (temperature, height, weight, blood pressure, pulse)
5. Review of concomitant medications and supplements
6. Review of adverse events
7. Patient questionnaires: DEBS, BIS, PGI-C, Q-LES-Q
8. Planning of transition of care.
9. Download of SAD daily scale data from website sad.ecu.edu.

Multiple potential referral options will be discussed, depending on the patient's improvement and insurance status. Final referral selected will be based on the patient's preference. Options include referral to a primary care physician, psychiatrist, therapist, community mental health center, or other research studies. If necessary, patients may be seen for 1 or 2 post-study follow-up visits until their care transfer is completed.

Schedule of Events:

BIS: Barratt Impulsiveness Scale; CSSRS: Columbia Suicide Severity Rating Scale; DEBS: Dunlop Emotional Blunting Scale; DESS: Discontinuation Emergent Signs and Symptoms; HAM-A: Hamilton Anxiety Rating Scale; MADRS: Montgomery Asberg Depression Rating Scale; MINI: Mini-International Neuropsychiatric Interview; PGI-C: Patient Global Impression, Change; PWC-20: Physician Withdrawal Checklist; Q-LES-Q: Quality of Life Satisfaction Questionnaire

Visit Number	V1	V2	V3	V4
Day	0	7	14	21
Informed consent	X			
Demographics	X			
Vital signs	X	X	X	X
Weight	X			X
Psych/Medical History	X			
MINI v.7.0	X			
Clinician Ratings				
MADRS	X	X	X	X

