The patient will be responsible for the cost of the antidepressant prescription (if necessary) and going to a pharmacy to get the prescription filled. Antidepressant medications eligible for discontinuation in this protocol include the SSRIs (citalopram, escitalopram, fluoxetine, fluvoxamine, paroxetine, sertraline, vilazodone or vortioxetine), SNRIs (desvenlafaxine, duloxetine, levomilnacipran, venlafaxine) and other classes (amitriptyline, bupropion, desipramine, doxepin, mirtazapine, nefazodone, nortriptyline, phenelzine, selegiline, or tranylcypromine). Clomipramine, a tricyclic antidepressant approved for the treatment of OCD, will also be included, but will be classed as an SSRI

for this study because inhibition of the serotonin transporter is its primary therapeutic mechanism.

Measures

Clinician-Rated:

1. The Mini International Neuropsychiatric Interview (MINI, Sheehan et al, 1998), will be used to assess psychiatric diagnoses, which will be confirmed by an interview with a study psychiatrist.
2. The Montgomery Asberg Depression Rating Scale (MADRS, Montgomery & Åsberg, 1979) will assess clinical depressive symptoms.
3. The Hamilton Anxiety Rating Scale (HAMA, Hamilton, 1959) will assess clinical anxiety symptoms.
4. The Discontinuation Emergent Signs and Symptoms (DESS, Rosenthal et al, 1998) questionnaire will assess the frequency of discontinuation symptoms.
5. The Physician Withdrawal Checklist (PWC-20, Rickels et al, 2008) will assess the intensity of discontinuation symptoms.
6. The Columbia Suicide Severity Rating Scale (CSSRS, Posner et al, 2007) will assess for the emergence of any suicidal ideation or behaviors during antidepressant tapering.

Patient-Rated:

1. The Barratt Impulsiveness Scale (BIS, Patton et al, 1995) will assess impulsivity.
2. The Dunlop Emotional Blunting Scale (DEBS) will assess for changes in emotional reactivity.
3. The Quality of Life Enjoyment and Satisfaction Questionnaire (Q-LES-Q, Endicott et al, 1993)
4. The Patient Global Impressions- Change (PGI-C) will assess the patient's overall perceived level of mental health compared to baseline.

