5. Scale for Anxiety and Depression (SAD). This 17-item scale is a self-report questionnaire asking about 17 common symptoms of depression over the past 24 hours and anxiety rated on a 1-10 visual analogue scale. The SAD is completed daily, providing a more fine-grained analysis of symptom change over short periods, such as tapering of antidepressants. The scale is accessed through a free internet app and takes approximately 3 minutes to complete.

Payment:

Patients will receive no compensation for participating in this study.

Outcomes:

Primary outcome:

The primary outcome is the change in the DESS, defined as the number of symptoms that are either new or worsened compared to baseline at Visit 4.

Secondary outcomes include:

1. Change in the PWC-20 from baseline to Visit 4
2. Number of patients who meet criteria for antidepressant discontinuation syndrome, defined as ≥ 4 new or worsened DESS symptoms, at visit during the study.

3. 3. Change in SAD daily score from baseline to peak SAD score during the taper period.

Statistical Analysis:

The primary analyses will be carried out on a modified intent to treat (ITT) sample, which will include all randomized patients who returned for at least one post-randomization study visit. The primary outcome variable is change in DESS score, defined as the number of symptoms that are either new or worsened at Visit 4 compared to baseline (Visit 1). For patients who terminate early the principle of last observation carried forward will be used. If amount of change for the total sample is non-normally distributed, raw change will be log-transformed to approximate a normal distribution before parametric tests are conducted. The primary analysis analyzing the taper groups will be an overall, 2-way ANCOVA, with appropriate covariates, on change in DESS score. Treatment groups will be compared on baseline variables that have a potential relationship to amount of change with the DESS. These include duration in months on ADM, dose equivalents of ADM at Visit 1, gender, age, Visit 1 HAMA score, Visit 1 MADRS score, and comorbid anxiety disorder. Only those Baseline variables that differ among randomized treatment groups at $P<0.10$ and are significantly associated with the primary outcome variable for the entire sample will be entered into the analysis as covariates.

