Secondary analyses will include a similar 2-way ANCOVA assessing change from baseline in PWC-20 and SAD peak daily scores between the two taper groups following the same analytic plan as for the DESS. The proportion of patients experiencing the ADM discontinuation syndrome in each taper arm will be compared by Chi-Square test. The frequency of individual discontinuation symptoms between the two taper arms will be assessed using Fisher's Exact Test.

Power Calculation:

An sample size of 48 patients per taper group provides 80% power to detect a clinically meaningful difference of 1.0 points on the DESS, with a standard deviation of 1.75 (at two-sided $\alpha=.05$). With 49 subjects per taper group, we will have 70% power to detect a difference of 20% (10% vs 30%) incidence in ADM discontinuation syndrome.

Adverse event reporting:

Risks to participation

Risks to participation include experiencing side effects from the taking or discontinuing antidepressant medications. All study antidepressants share some risks, including headache, nausea, anxiety, sleep and appetite disturbance. In patients under age 25, antidepressant initiation and dose increase has been associated with a small increased risk of developing thoughts of self-harm or suicidal ideas.

Benefits to subject or future benefits

Patients who participate will receive an expert psychiatric assessment and treatment. With treatment, patients may be able to come off ineffective or no longer desired antidepressant medication. Patients will have the benefit of participating in a clinical trial that could inform future treatment of patients with antidepressants.

Training:

No training will be necessary for the rating scales used in this study because all research personnel involved in this project as they are currently trained and involved in ongoing clinical trials with mentally ill patients.

Confidentiality:

Patient's confidentiality will be maintained throughout the duration of their study participation. Patient files will be kept in locked offices, and the computerized data is kept on password-protected computers in the locked Mood and Anxiety Disorders Program offices.

Informed consent:

At the screening visit, patients will be provided with an informed consent form that will outline the risks and benefits of participating in this study. It will also outline which assessments occur at the various study visits.

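### Change in PWC-20 from baseline to Visit 4 (secondary outcome 1) cannot be computed, because no PWC-20 is scheduled at Visit 1

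*Combined protocol and SAP*

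**What the plan says.** - **Outcomes, secondary item 1:** "Change in the PWC-20 from baseline to Visit 4".
- **Statistical Analysis, secondary analyses:** a two-way ANCOVA "assessing change from baseline in PWC-20 and SAD peak daily scores between the two taper groups", under the same plan as the DESS. The DESS plan identifies baseline as Visit 1.
- **Procedures, Visit 1, item 5:** "Clinician assessment of discontinuation symptoms present at baseline: DESS". None of the 12 Visit 1 items mentions the PWC-20. Randomisation follows at the end of this visit.
- **Procedures, Visits 2, 3 and 4, item 3:** "Clinician assessment of discontinuation symptoms: DESS, PWC-20".
- **Schedule of Events:** the PWC-20 row is blank at V1 and marked at V2, V3 and V4. The DESS row is marked at all four visits.
- **Measures:** the PWC-20 "will assess the intensity of discontinuation symptoms". The PGI-C, which is also first given at Visit 2, rates the patient's "overall perceived level of mental health compared to baseline".

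**The concern.** A change score needs a value at both ends, and the PWC-20 has only the later one. The Measures section gives the DESS the task of counting discontinuation symptoms and the PWC-20 the task of grading their intensity. The endpoint that fails is therefore the change from baseline on the only scale described as measuring intensity.

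If the text stays as it is, the analyst must choose a definition after the data are in: the Visit 4 score alone, change from Visit 2, or change from an assumed zero. These can give different answers, and the choice could be made with results in view. A pre-taper PWC-20 cannot be recovered once a patient has started the taper.

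**Working it through.** **1. Availability of the score.** Scheduled PWC-20 assessments are V1 = 0, V2 = 1, V3 = 1, V4 = 1. Pre-taper values per patient = 0, so PWC-20(V4) − PWC-20(V1) is undefined for all patients. The visit lists and the schedule table are separate parts of the document and agree, so the blank cell is not a table-extraction fault.

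**2. Could something else serve as baseline?**
- *Visit 2.* The documents do not propose it. It falls after randomisation and a week into the taper. Under Taper Regimens the arms already differ by then: on days 4–7 Taper A is at 50% of baseline dose and Taper B at 25%. Subtracting a Visit 2 score could remove part of the effect under study.
- *An assumed zero.* This is not stated either. The plan itself rates the DESS for symptoms already present at Visit 1. Enrolled patients have depressive, anxiety, obsessive-compulsive or post-traumatic disorders, whose symptoms overlap with the listed discontinuation symptoms (mood, anxiety, irritability).
- *A scale that rates change directly.* The PGI-C is described that way and needs no Visit 1 value. The PWC-20 is described as an intensity measure.

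**3. What the missing baseline costs in precision.** The plan has no power figure for the PWC-20. Its DESS figure calibrates the method: a difference of 1.0 with SD 1.75 is 1.0/1.75 = 0.571 SD, and 48 per group gives 79.9% power by the normal approximation and 79.1% by the t test, against 80% stated.

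Inputs: 48 per arm, 80% power, two-sided 0.05 (from the Power Calculation), and an assumed correlation r between the Visit 1 and Visit 4 PWC-20.

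- Visit 4 score alone: detectable difference 0.578 SD (t test).
- Visit 4 score adjusted for baseline PWC-20: variance is multiplied by (1 − r²), so the detectable difference is 0.578 × √(1 − r²).
- Unadjusted change score: relative variance is 2(1 − r) if the variance is the same at both visits, so the detectable difference is 0.578 × √(2(1 − r)).

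| Assumed r | Visit 4 only | Baseline-adjusted (variance factor) | Unadjusted change (variance factor) |
|---|---|---|---|
| 0.3 | 0.578 | 0.551 (0.91) | 0.684 (1.4) |
| 0.5 | 0.578 | 0.500 (0.75) | 0.578 (1.0) |
| 0.7 | 0.578 | 0.413 (0.51) | 0.448 (0.6) |

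The adjusted analysis is the most precise at each of these correlations. The unadjusted change score beats the Visit 4 score only if r exceeds 0.5.

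**The case against.** The contradiction itself is hard to dispute. The best case against the point concerns its weight.

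- *The precision loss is measured against an analysis the plan never proposed.* This is fair. The plan analyses the change score, and baseline PWC-20 is not among its candidate covariates. Against an unadjusted change score, the Visit 4 comparison loses nothing at r = 0.5 and gains at r = 0.3. The loss shown is relative to the analysis that a Visit 1 measurement would make possible.
- *The change-score column needs equal variance at Visits 1 and 4.* This is also fair, since the documents give no PWC-20 variance. The baseline-adjusted column does not need that assumption.
- *A Visit 4 comparison is not free of bias in general.* Early withdrawal handled by last observation carried forward, and raters whose blinding is not described, could still bias it. That stands, but those problems would exist with a baseline too. The narrower claim is that lacking the baseline does not bias a comparison of randomised arms.
- *The PWC-20 form is not reproduced in the text available, so reading it as an absolute score is an inference.* It is one, from the description in Measures and the contrast with the PGI-C.
- *Other scales with Visit 1 values (MADRS, HAMA, SAD) grade mood and anxiety.* They do, which softens the consequence. None of them is described as a measure of discontinuation-symptom intensity.

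None of these supplies the missing Visit 1 value.

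**Conclusion.** The concern holds. Secondary outcome 1 is undefined for every patient as the plan is written. It is one of four named outcomes (one primary, three secondary). The primary DESS outcome, the discontinuation-syndrome outcome and the SAD outcome all have Visit 1 measurements, and no power statement depends on the PWC-20.

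This should be fixed, but it does not threaten the trial's main conclusion. The core finding rests only on the schedule, the visit lists and the description of the scale. The precision figures depend on assumed correlations and are there to guide the choice of repair.

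**What to change.** **Preferred.** Add the PWC-20 to Visit 1, before randomisation, in both the procedure list and the V1 column of the schedule. Name baseline PWC-20 as a prespecified covariate in the PWC-20 ANCOVA.

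**If any patients have already been enrolled without it.** Use one definition for all patients: the Visit 4 PWC-20 score compared between arms, adjusted for the Visit 1 DESS, with early termination handled as for the DESS. State that the Visit 1 DESS here means the count of symptoms present at Visit 1, because the plan defines a DESS score only as change from baseline.

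**In either case.** State that the covariate is a prespecified exception to the selection rule in Statistical Analysis, which admits a baseline variable only if it differs between arms at P<0.10 and is associated with the outcome. The secondary analyses inherit that rule, and it could otherwise drop the covariate.

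**Cost.** The preferred fix takes one extra clinician checklist at a visit where a clinician already rates the DESS (the documents give no completion time), and a short amendment to the Visit 1 list, the schedule and the secondary-analysis text. The fallback needs no new data, but it requires rewording the outcome, gives up the change score, and is probably less precise than adjusting for baseline PWC-20.

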A Comparison of Two Antidepressant Tapering Regimens

29 January 2016

NCT02661828

Full Title: A Comparison of Two Antidepressant Tapering Regimens

Short Title: Tapering off Antidepressants

Principal Investigator: [name]

Co-Investigator: [name]

Draft Date: January 29, 2016

Precis/Abstract:

One hundred adults currently taking an antidepressant for at least four weeks for the treatment of major depressive disorder, an anxiety disorder, obsessive compulsive disorder (OCD) or posttraumatic stress disorder (PTSD) will be randomly assigned to receive one of two different medication tapering regimens. The study will aim to characterize: 1) the clinical characteristics predictive of antidepressant discontinuation symptoms; and 2) which of two tapering regimens is more effective at minimizing antidepressant discontinuation symptoms. Participants will be enrolled in this study ONLY if they no longer wish to take the antidepressant medication they are currently prescribed, due to one of the following reasons: 1) ineffective for symptoms; 2) intolerable side effect; 3) improvement of their illness for sufficient duration that it is clinically appropriate to consider tapering the medication. The study will consist of 4 study visits. At the first visit, all participants will complete a psychiatric interview and questionnaires. The subsequent visits will involve assessment of discontinuation symptoms and mental health symptoms. Upon completion of the antidepressant taper, patients will be assisted in pursuing options for additional treatment if required.

Introduction and Background:

It is widely recognized that abrupt cessation of antidepressant medication (ADM) causes distressing symptoms (known as antidepressant discontinuation symptoms). Discontinuation symptoms can occur regardless of the diagnosis under treatment, whether major depressive disorder (MDD), an anxiety disorder, obsessive compulsive disorder (OCD) or posttraumatic stress disorder (PTSD). These symptoms vary substantially in character, intensity and duration, and there are currently no reliable means of predicting which patients will experience discontinuation symptoms. In most cases these symptoms last less than one week, but occasionally can persist for weeks to months (Fava et al, 2015).

The rates of ADM discontinuation symptoms are not consistent across studies, but the most frequent are as follows:

Symptom	% Patients Experiencing
Worsened mood:	22-45

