Clinical practice would be enhanced if predictors of difficulty tapering ADM could be identified. Currently, very little is known about which patients are likely to develop discontinuation symptoms. The most consistently replicated finding is that the long half-life antidepressant fluoxetine is associated with fewer discontinuation symptoms than the short half-life agent paroxetine. However, discontinuation symptoms are known to arise with fluoxetine cessation, and both these drugs are SSRIs. Identification of patients who will or will not develop difficulty coming off antidepressants is of significant clinical importance because tapers that are longer or shorter than necessary can negatively impact patient care.

This study will aim to assess the frequency of discontinuation symptoms across all classes of antidepressants among patients who have not responded to medication. Only patients who wish to be tapered off their medication will be eligible to participate.

Objectives:

There are two primary objectives to this study:

AIM 1: Compare the tolerability of two antidepressant tapering regimens.

Hypothesis 1. Tapering antidepressant dose over two weeks will be associated a lower incidence of antidepressant discontinuation symptoms than tapering over one week.

Hypothesis 2. Discontinuing medications that inhibit the serotonin transporter (SSRIs and SNRIs) will show greater difference in the frequency of discontinuation symptoms between the two week and one-week tapering regimens than medications that do not inhibit the serotonin transporter.

AIM 2: Identify demographic and clinical features that predict the emergence of antidepressant discontinuation symptoms.

Hypothesis 2. SSRIs and SNRIs will be associated with greater numbers of discontinuation symptoms compared to non-SSRI/SNRI medications.

Hypothesis 1. Duration of treatment will positively associated with the number of discontinuation symptoms.

Study Design and Methods:

Sample

The sample will include 125 subjects currently taking an FDA-approved antidepressant. We anticipate an approximate screen fail rate of 20%, allowing for 100 subjects to enter randomization.

Inclusion Criteria:

1. Male or female, age 18-75
2. Currently taking an FDA-approved antidepressant for at least four weeks.
3. Primary psychiatric diagnosis of major depressive disorder, an anxiety disorder, OCD, or PTSD.
4. Ability to read and understand English language

Exclusion Criteria for all Subjects:

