HAMA	X	X	X	X
DESS	X	X	X	X
PWC-20		X	X	X
Patient Ratings				
DEBS	X	X	X	X
BIS	X	X	X	X
Q-LES-Q	X			X
PGI-C		X	X	X
SAD (Daily)	X	X	X	X
Safety Measures				
Concomitant Meds	X	X	X	X
Adverse Events		X	X	X
CSSRS	X	X	X	X

Taper Regimens:

Taper A:

Days 1-7: Take 50% of baseline dose
Days 8-14: Take 25% of baseline dose
Day 15: Stop antidepressant

Taper B:

Days 1-3: Take 50% of baseline dose
Days 4-7: Take 25% of baseline dose
Day 8: Stop antidepressant

Monitoring for Suicidality

The emergence of suicidal thoughts or behaviors are not considered part of antidepressant discontinuation symptoms, but rather are thought to reflect the breakthrough of a new depressive episode. Patients who do not believe their antidepressant is helping them may nevertheless experience worsening depression with discontinuation of the medication. Therefore, we will conduct a standardized assessment for suicidal ideation or behavior, the CSSRS, at every study visit. Any patient who exhibits and increase in suicidal ideation, any form of suicidal behavior, or about whom the study physician has concern for their safety will be immediately withdrawn from the study and treated as clinically appropriate.

Operationalized Discontinuation Criteria for Suicidality:

Research participants are exited from the study should any of the following occur:

- Any emergent CSSRS defined suicidal behavior
- A suicidal ideation score of 5 (indicating active suicidal ideation with specific plan and some level of intent) on the CSSRS
- In the absence of a CSSRS suicidal ideation score of 5 or CSSRS-defined suicidal behavior, the investigator determines the patient to have a significant short-term risk for a suicide attempt.

Randomization:

Patients will be randomized in a 1:1 manner to Taper A or Taper B. Randomization will be stratified based on mechanism of action of drug (serotonin reuptake inhibitor or not). The two randomization schedules will be created prior to study commencement by a staff member not involved in the clinical components or data analytic components of the study. Randomization assignments will be placed in numbered and sealed envelopes, and opened sequentially for each subject who qualifies for randomization at Visit 1.

Included Medications:

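### The SAD secondary outcome is a peak over an undefined taper period; on its plain reading that is 14 days in Taper A and 7 in Taper B, which biases the comparison against Taper A

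*Combined protocol and SAP*

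**What the plan says.** Outcomes, secondary item 3, defines the endpoint as "Change in SAD daily score from baseline to peak SAD score during the taper period". The Statistical Analysis section plans a two-way ANCOVA of "change from baseline in PWC-20 and SAD peak daily scores between the two taper groups", handled as for the DESS. It gives no window and no allowance for the number of days scored.

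No section assigns days to the taper period. The nearest text is:

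- Objectives, Aim 1, Hypothesis 1: "Tapering antidepressant dose over two weeks will be associated a lower incidence of antidepressant discontinuation symptoms than tapering over one week".
- Taper Regimens: "Day 15: Stop antidepressant" for Taper A and "Day 8: Stop antidepressant" for Taper B.
- Outcomes, secondary item 2, which uses a different phrase for its window: "new or worsened DESS symptoms, at visit during the study".
- Procedures, Visit 1: "participants will complete the SAD daily until Visit 4". Visit 4 is on Day 21 in both arms, so a common 21-day series exists, but the outcome is not tied to it.

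**The concern.** A maximum tends to grow with the number of observations it is taken over. If the taper period means the days on a reduced dose, the arm with the longer taper gets twice as many chances to record a bad day. Two equally tolerated tapers would then give a SAD comparison that leans against the two-week taper, the opposite direction to Hypothesis 1, and a real benefit of that taper could be masked. Covariate adjustment cannot repair this, because the bias lies in how the outcome is defined.

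The same reading discards every off-drug score (Days 15–21 in Taper A, Days 8–21 in Taper B). These are collected, and they cover the time when symptoms caused by stopping would appear.

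**Working it through.** **No plan figure to reproduce.** The document states no SD, effect size or power for the SAD. Its power figures concern the DESS and the discontinuation syndrome and do not bear on this point.

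**Inputs from the document.** Reduced dose on Days 1–14 (Taper A) and Days 1–7 (Taper B), from Taper Regimens; daily SAD to Day 21, from Procedures and Schedule of Events; 100 randomized 1:1, so 50 per arm.

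**Assumptions not in the document.** Daily scores are normal with within-patient SD 1 and first-order autoregressive correlation ρ from 0 to 0.9. Diaries are complete. There is no taper effect. The comparison is a two-sided 5% t-test on peak minus Day 0 score, standing in for the planned ANCOVA. Where stated, patients also differ in true change with between-patient SD *s*, in units of the within-patient SD.

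**Step 1: expected peak, independent days.** For k scores, E[max] = ∫ x·k·φ(x)·Φ(x)^(k−1) dx. This gives 1.352 for k = 7, 1.703 for k = 14 and 1.889 for k = 21. The excess for Taper A is 1.703 − 1.352 = 0.351 SD.

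**Step 2: false finding that Taper A is worse, ρ = 0.** The simulated SD of the maximum is 0.555 over 14 days and 0.626 over 7 days. The independent Day 0 score adds variance 1, so the variance of change is 0.308 + 1 = 1.308 (A) and 0.392 + 1 = 1.392 (B). The standard error is √((1.308 + 1.392 + 2s²)/50), and the critical t on 98 df is 1.984.

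| s | SE | 0.351/SE | P(Z > 1.984 − 0.351/SE) |
|---|---|---|---|
| 0 | 0.232 | 1.51 | 32% |
| 1 | 0.307 | 1.14 | 20% |
| 2 | 0.463 | 0.76 | 11% |
| 3 | 0.643 | 0.55 | 8% |

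The nominal rate in this direction is 2.5%.

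**Step 3: correlated days** (simulated series, noncentral t).

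| ρ | Excess for Taper A (SD) | False 'A worse', s = 0 |
|---|---|---|
| 0 | 0.35 | 32% |
| 0.3 | 0.37 | 36% |
| 0.5 | 0.40 | 42% |
| 0.7 | 0.40 | 48% |
| 0.9 | 0.33 | 54% |

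Over the same range of ρ the rate is 21–28% at s = 1, 11–14% at s = 2 and 7–9% at s = 3. Simulating whole trials at s = 0 gives 31–52%. Adding the Day 0 score as covariate does not help: it shrinks the residual variance but not the bias, and the rates become 69–84%, 27–37%, 13–15% and 8–10% for s = 0, 1, 2 and 3.

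**Step 4: masking.** Suppose Taper B is truly worse by 0.35 SD on every day. The expected A − B difference is the excess minus 0.35, which runs from 0.33 − 0.35 = −0.02 to 0.40 − 0.35 = +0.05. At s = 0, power to show Taper B worse is about 1–4%, against 34–46% with Days 1–21 in both arms.

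**Step 5: common window.** With Days 1–21 in both arms and no effect, the mean difference is within 0.005 SD of zero and the two-sided error is 4.3–5.2%, nominal within simulation error.

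**The case against.** The strongest reply is that the document also uses the word taper loosely for the whole study. The Precis has patients helped towards further treatment once the taper is complete, and that step is scheduled at Visit 4, Day 21 in both arms. The Measures section says the CSSRS looks for suicidality during tapering, yet it is given at every visit to Day 21. Item 2, which uses a different phrase, is itself garbled and so is weak evidence of a deliberate contrast. This stands: the phrase is ambiguous, and on the whole-study reading the bias is absent. It does not make the text safe, because Hypothesis 1 and the regimens support the unequal windows, and an unstated window can be chosen after the data are seen.

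Second, the highest false-positive rates need every patient to have the same true change, which is hard to believe given the range of eligible drugs. That is fair; the rates at s = 1 to 3 are the more credible ones, and they still exceed 2.5%.

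Third, the masking example uses an effect about equal to the artefact, so cancellation is built in. Also true. A real 1.0 SD effect at s = 0 would still be found with 77–99% power under the unequal windows. At s = 2, even Days 1–21 has only 11–12% power for 0.35 SD. Masking matters for effects near the size of the artefact.

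Fourth, Days 1–21 is not neutral about off-drug time. This is right, and is dealt with under the remedy.

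**Conclusion.** The concern holds. That the window is undefined is certain. The bias is conditional on reading the taper period as the days of dose reduction, which is what the regimens and Hypothesis 1 describe. On that reading Taper A's peak is higher by 0.33–0.40 within-patient SD in expectation with no taper effect, and the direction is the same at every correlation tried. How often this produces a false result depends on between-patient variation that the document does not give: from about 32–54% at s = 0 down to 7–9% at s = 3. The bias cannot be expressed in SAD points without a SAD SD.

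The harm is confined to this one secondary outcome. The primary DESS outcome, the discontinuation syndrome and the PWC-20 do not use this window, and the DESS and PWC-20 still capture off-drug symptoms at Visit 4. It should be fixed before analysis.

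**What to change.** Define the outcome as the change from the Visit 1 SAD score to the highest daily SAD score from Day 1 to Day 21 (Visit 4) in both arms, with the Visit 1 SAD score as covariate. If that was always the intention, the text need only say so.

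Add to the analysis section:

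- A sensitivity analysis of the peak over the first seven off-drug days in each arm (Days 15–21 in Taper A, Days 8–14 in Taper B), repeated with the mean daily score, which does not grow with the number of days scored.
- The number of scored diary days per arm, including for early withdrawals. Under Days 1–21, random missingness of 10% in one arm and 30% in the other creates a false difference of 0.06–0.12 SD.

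The cost is one sentence in the outcome definition and two in the analysis section, with no new data.

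The downside is that Days 1–21 equalises total days but not off-drug days: 7 in Taper A, 14 in Taper B. If stopping raises SAD equally in both arms and the rise lasts to Day 21, Taper B's peak is higher by 0.23–0.28 SD for a 1 SD rise and 0.31–0.38 SD for a 2 SD rise, which favours Hypothesis 1. If the rise resolves within a week the difference is under 0.04 SD, and the Introduction describes that as the usual course: "In most cases these symptoms last less than one week, but occasionally can persist for weeks to months". The seven-day off-drug analysis brings the difference to 0.01 SD or less in both cases, but it ignores symptoms that appear during dose reduction. It therefore belongs beside the 21-day definition, not in place of it.
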